	
Control intervention (1): 12 sessions (60 min) over 8 weeks of electroencephalography (EEG) neurofeedback (high beta training)
 
Control (2): 8 weeks without treatment, after which 12 sessions (60 min) over 8 weeks of fNIRS neurofeedback will be offered (delayed treatment control condition)

Primary outcome:	The number of objective binge-eating episodes (OBEs) over the past 14 days at post-treatment (t1), derived from the Eating Disorder Examination, will be compared between groups, correcting for the baseline value
Secondary outcome:	
 
- Feasibility including recruitment, attrition, assessment completion, patients' program evaluation
 
- Eating disorder psychopathology
 
- Executive functioning
 
- Weight management behavior
 
- Mental and physical health
 

Biometry:	
Efficacy / test accuracy: The comparison between the groups with respect to binge eating episodes directly after treatment.
 
Safety: Report of type and frequency of adverse events.
 
Secondary endpoints: Descriptive analyses, effect sizes, presented with 95% confidence intervals, parametric or non-parametric tests, regression analyses.

Trial duration:	
Duration of intervention per patient: 8 weeks
 
Follow-up per patient: 6 months
 
First patient in to last patient out (months): 25 months
 
Duration of the entire trial (months): 30 months
 
Recruitment period (months): 17 months

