Intervention. *fNIRS neurofeedback:* The fNIRS neurofeedback training will be delivered in 12 individual sessions (60 min) over 8 weeks. Personally salient binge food stimuli (and matched neutral stimuli, i.e., household items) will be pre-selected from validated databases. The fNIRS neurofeedback protocol will include a *localization trial* at the outset, during which the individual target area in the prefrontal cortex (e.g., dorsolateral, orbitofrontal) that demonstrates reliable activation differences in response to food stimuli compared to rest, will be selected for training (region of interest, ROI). Detailed working instructions will be derived from pilot measurements. The localization trial will include a rest period, a perceptual food cue exposure (“watch”), a craving food cue exposure (“allow yourself to crave”), and a perceptual neutral cue exposure (household items). The *neurofeedback trials* will include a rest period and regulation food cue exposure (“reduce craving”), followed by rest and reinforcement. During food cue exposure, each food cue

is presented with variable size according to the change in percent blood oxygenation level dependent signal, relative to the preceding fixation block. The goal is to reduce craving by decreasing the size of the food cue. For optimal learning, cognitive-behavioral techniques will be used such as information, reinforcement and self-reinforcement, guided discovery of self-regulation skills, cognitive restructuring, goal setting and planning of transfer into daily life, and homework assignments.

Control. Two control conditions will be used: (1) *EEG neurofeedback*: A validated food cue-based EEG training protocol (high beta training) will be used with 12 individual sessions (60 min) over 8 weeks. This condition serves to examine the comparative efficacy and specificity of changes. (2) *Delayed treatment control condition*: The untreated group will not receive any treatment over 8 weeks, but will afterwards be offered fNIRS neurofeedback. This control condition is essential for examining basic efficacy.

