## 5.4 Description of the study procedure

Following the baseline visit including randomization (see 5.3), patients will receive active treatment or control (fNIRS neurofeedback/EEG neurofeedback) or delayed treatment which involves a period of 8 weeks without treatment. If a patient was randomized into the delayed treatment condition, the following variables will be assessed prior to the treatment 8 weeks after randomization:

Time point	Variable
Only delayed treatment  Before start of therapy Week 8 (+ max. 2 weeks)	
 
Anamnesis
 
Comorbidities
 
Medication intake
 
Anthropometry
 
Sociodemographics
 
Eating disorder psychopathology e.g., Eating Disorder Examination (EDE)
 
General psychopathology e.g., Patient Health Questionnaire (PHQ)
 
Neuropsychological and brain activity-related measures e.g., Go/NoGo task
 
Behavioral measures e.g., Bogus taste test
 
Visual analogue scales (VAS): expectations, motivation
 

During treatment, all patients will be assessed weekly (i.e. at each treatment session), including the following variables:

Time point	Variable
During treatment, weekly Active treatments: Weeks 1-7 Delayed treatment: Weeks 9-15	
 
Brain activity-related outcomes e.g., EEG frequency band power
 
Visual analogue scales (VAS): state craving, liking, sense of control, hunger, satiety, and mood
 
Objective binge-eating episodes
 
(Serious) adverse events
 

The following variables will be assessed at the end of treatment, 8 (fNIRS neurofeedback and active control treatments) or 16 (delayed treatment control condition) weeks after randomization.

Time point	Variable

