### 2.2 Secondary endpoints (Item 6a of the CRED-nf checklist)

Unless otherwise indicated, the scores from questionnaires are calculated using the “qscorer” package from [name] (see appendix for code). Comparisons between all three groups are foreseen at T0 (baseline) and T1/T0WL. After T0WL, the WL control group received an fNIRS intervention. Hence, T2 can only be used to estimate changes within a group and between the two intervention groups.

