## d) Brain-activity-related outcomes

- fNIRS and fNIRS delayed treatment group, group-wise: Condition-(neurofeedback/transfer), block(first block/second block) and task-wise (regulation/mirror/rest) oxygenated, deoxygenated, and total haemoglobin values per session for the 2 individual fNIRS channels that were selected for training and for regions of interest.
- EEG group only (T0, T1): Eyes-closed (3min) and eyes-open (3min) resting-state and food-specific activity (90s) for theta, alpha, and beta band in  $\mu\text{V}$
- EEG group only: mean beta activity baseline and feedback in  $\mu\text{V}$  per session noted from TheraPrax device, amount of successful trials and % success in transfer trial per session

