## 3 General analysis definitions

### 3.1 Analysis populations

Analysis of the primary and secondary outcomes are based on the full analysis set (FAS). Note that patients fulfilling the criterion for abstinence at T0 will not be included in the analysis for this endpoint. Further, the analysis of the primary outcome will be performed in the per-protocol set (PPS) to evaluate the treatment effect for patients with good protocol adherence, if FAS and PPS comprise a sufficiently different set of patients. Analysis of the fNIRS data will be performed in the fNIRS data set.

The FAS includes all randomized patients unless purely technical issues precluded the fNIRS measurements. In particular, three patients had to be replaced because of the aforementioned technical issues with fNIRS. Patients who could not complete the intervention due to the SARS-CoV-2 situation will be retained in the FAS if they completed at least 5 sessions and provided OBE data at T1. In control patients, those who could not attend T0WL due to SARS-CoV-2 will not be retained in the FAS.

The PPS includes all patients of the FAS without serious violations of the study protocol. The following protocol violations are classified as serious:

- Violation of at least one inclusion or exclusion criterion

- Treatment was not conducted as mandated, that is
  - Temporal delay of last attended treatment session by 4 weeks relative to the planned date, `exdat`, (based on the date of the first treatment session). Note that consideration of a maximum of two weeks' delay in each session as originally foreseen was not considered feasible.
  - Absence of more than 6 of the planned 12 treatment sessions (based on `meet`)
- Use of forbidden medication
- Psychological treatment during study participation (was not the case, otherwise it would be documented in the "comments")

The fNIRS/EEG data set includes all patients from the fNIRS/EEG group of the FAS who provided data for more than a single neurofeedback session. Participants with fewer sessions are excluded from the analyses, because the definition of neurofeedback *training* does not apply for these participants and there is no information on between-session variability.

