### **4.3.3 Correlation between regulation and outcomes for patients who provided data for at least two feedback sessions (CRED-nf 6b)**

A linear model will be used with the number of OBEs at post-assessment as the dependent variable, the value at T0 as covariate and mean picture size across all sessions as the variable of interest.

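### SAP 2.2 d declares fNIRS outcomes for the delayed-treatment arm, but SAP 3.1 read literally leaves that arm out of the fNIRS data set, and 4.3.3 has no suitable baseline for it.

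*SAP*

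**What the plan says.** The protocol synopsis describes the third arm as "8 weeks without treatment, after which 12 sessions (60 min) over 8 weeks of fNIRS neurofeedback will be offered", and Protocol 1.2.1 says the same: "The untreated group will not receive any treatment over 8 weeks, but will afterwards be offered fNIRS neurofeedback". SAP 2.2 confirms that it happened: "After T0WL, the WL control group received an fNIRS intervention". Protocol 5.4 schedules weekly brain-activity data during the course ("Delayed treatment: Weeks 9-15"), an EDE interview before the course at week 8 and another at its end at week 16.

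SAP 2.2 d gives the haemoglobin outcomes per session for "fNIRS and fNIRS delayed treatment group, group-wise". SAP 3.1 then states: "Analysis of the fNIRS data will be performed in the fNIRS data set". It defines that set by saying that the fNIRS/EEG "data set includes all patients from the fNIRS/EEG group of the FAS who provided data for more than a single neurofeedback session".

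SAP 4.3.1 to 4.3.3 do not say which arms enter. The regulation-outcome model in 4.3.3 has OBEs at post-assessment as the dependent variable, with "the value at T0 as covariate and mean picture size across all sessions as the variable of interest". Section 4.3 opens by calling itself provisional, pending the next SAP version.

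**The concern.** An outcome is declared for two groups, but the analysis set for that outcome names only one. In 2.2 d the fNIRS group and the delayed group are listed separately, so the fNIRS group in 3.1 does not naturally cover both. The choice of arms could then be made after the data are seen.

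Both readings cost something. If the delayed arm is out, patients with the same 12-session course, session recordings and EDE interviews before and after it contribute nothing to the learning analyses (4.3.2) or the regulation-outcome model (4.3.3). Those analyses ask what happens within trained patients, so they do not need concurrent randomised groups. If the delayed arm is in, 4.3.3 as written adjusts its patients for an OBE count taken before an untreated waiting period rather than just before training.

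**Working it through.** **Setting the texts side by side**

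| Place | Who is covered |
|---|---|
| SAP 2.2 d | fNIRS arm and delayed arm, by group |
| SAP 3.1, fNIRS data set | fNIRS group of the FAS with more than one session |
| SAP 4, introductory text | patients with data on at least two sessions; no arm named |
| SAP 4.3.1 to 4.3.3 | no arm named |
| SAP 4.3.3 covariate | OBEs at T0; no T0WL term |

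SAP 2.2 d and 3.1 conflict on a literal reading, and 4.3 does not settle it.

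**Inputs**
- 26 randomised per arm, 1:1:1 (synopsis; Protocol 7.1).
- 20% drop-out (Protocol 7.4.3): 26 × 0.8 = 20.8, about 21, which agrees with the 21 analysed in the waiting group in Protocol 7.4.4.
- The documents give no size or power target for the fNIRS data set, so there is no plan figure to reproduce.
- Assumptions: uptake u among delayed patients (100% or 50%), a true partial correlation of 0.40, and two-sided alpha of 5%. None of these comes from the documents for this analysis.

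**Share of fNIRS-treated patients left out** = u / (1 + u)
- u = 100%: 26 / 52 = 50%
- u = 50%: 13 / 39 = 33%

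**Illustrative power for 4.3.3**, by Fisher's z: power = Φ(atanh(0.40) × √(n − 3 − k) − 1.96), where k is the number of covariates and atanh(0.40) = 0.4236. The immediate arm alone has k = 1 (baseline OBE). The pooled model has k = 2 (baseline OBE and the immediate/delayed term).

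| Data set | n | k | √(n − 3 − k) | Power |
|---|---|---|---|---|
| Immediate only, no drop-out | 26 | 1 | √22 = 4.690 | Φ(0.027) = 51% |
| Pooled, full uptake, no drop-out | 52 | 2 | √47 = 6.856 | Φ(0.944) = 83% |
| Immediate only, 20% drop-out | 21 | 1 | √17 = 4.123 | Φ(−0.213) = 42% |
| Pooled, full uptake, 20% drop-out | 42 | 2 | √37 = 6.083 | Φ(0.617) = 73% |
| Pooled, half uptake, 20% drop-out | about 31 | 2 | √26 = 5.099 | Φ(0.200) = 58% |

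For the last row, 21 + 0.5 × 21 = 31.5, taken as 31. No corresponding figure was derived for the repeated-measures models in 4.3.2.

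**The case against.** The strongest reply is that exclusion is not established. SAP 2.2 d names the delayed arm, the introduction to section 4 restricts these analyses by number of sessions and not by arm, and 4.3 is openly provisional. This stands: a reader might infer from 3.1 that the models never use the delayed patients, but the documents support only an unresolved conflict.

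A reader might also infer that 4.3.3 would take T0WL, a pre-treatment value, as the delayed patients' outcome, because SAP 2.1 makes T0WL their primary follow-up value. The text does not support that. SAP 2.1 and 4.1 distinguish the post-assessment value from the post-waiting value, and 4.3.3 mentions only the former. Only the covariate problem remains, and a T0-only covariate would also fit a deliberate restriction to the immediate arm.

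Pooling is not free of assumptions. Delayed patients start after eight untreated weeks, and those who take up the offer are self-selected. A group term absorbs a difference in mean level. It neither removes the selection nor makes the regulation-outcome slopes equal. The SARS-CoV-2 rules for staying in the FAS also differ between intervention and control patients. Reporting each group separately, as 2.2 d words it, is therefore a legitimate alternative, and the fix keeps it.

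Finally, these analyses are exploratory and brain activity is one secondary outcome among many. That limits the importance of the point but does not remove the conflict.

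**Conclusion.** The point holds as an inconsistency between SAP 2.2 d and 3.1 that 4.3 leaves open, with a drawback under either reading. On the literal reading, between 33% (half uptake) and 50% (full uptake) of fNIRS-treated patients drop out of the regulation and regulation-outcome analyses. It would be wrong to read this as half of all treated patients: the EEG arm is also treated, and 50% requires every delayed patient to take up the offer, which is not documented. If the delayed patients are included, the covariate in 4.3.3 is wrong for them.

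The power gain is an illustration. It rests on an assumed correlation of 0.40 and covers 4.3.3 only, and at half uptake with drop-out it is modest (42% to about 58%). The primary endpoint and the confirmatory comparisons are unaffected. This is a cheap improvement, and the announced next SAP version is the natural place for it.

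**What to change.** - **SAP 3.1:** define the fNIRS data set as all FAS patients who received fNIRS neurofeedback, immediate or delayed, with data from at least two sessions.
- **SAP 4.3.2 and 4.3.3:** add a fixed term for immediate versus delayed treatment, and also report results by group, in line with 2.2 d.
- **SAP 4.3.3:** use the last OBE value before the course as covariate (T0 for immediate, T0WL for delayed patients) and T1 at the end of the course as outcome (week 8 or week 16).
- **Sensitivity analysis:** repeat with the immediate arm alone. Report how many delayed patients took up the course, and state that they are self-selected.

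If the sponsor prefers to exclude the delayed arm, 3.1 should say so with a reason, and 2.2 d should be aligned.

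The cost is SAP wording, one extra model term (one degree of freedom) and one sensitivity run. All the data are already scheduled.

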### 3.2 Subgroups

No subgroups will be analysed.

## 4 Planned analysis

A flowchart according to the CONSORT statement will describe all patients randomized to the trial detailing withdrawals, drop-outs and inclusion in the analysis sets defined above. It will also provide details regarding treatment and assessment completion.

Standard methods of descriptive statistics will be used always indicating the number of valid values; frequencies, mean (standard deviation), minimum, maximum and/or quartiles (median [25%; 75%]), depending on the scale and distribution within the study population and/or per arm will be provided. Summary statistic will be reasonably rounded to avoid pseudo-precision. Reliability (Cronbach's  $\alpha$ ) will be calculated for each psychometric scale at T0.

For the explorative neurophysiological analyses, only completer analyses will be considered and in patients who have provided neurophysiological data on at least two sessions. There the primary focus is on understanding neurophysiological processes in those that complete the training sessions and its potential effect on outcome.

### 4.1 Primary endpoint

The primary endpoint, the number of OBEs at post-assessment or post-waiting, will be analysed using ANCOVA with OBEs as the dependent variable, OBEs at T0 as a covariate as well as the stratification criteria (`strabmi`, `stralsex`, `strawei`). The code for this test will have the structure

```
anova(lm(OBE_FU ~ OBE_T0 + STRABMI + STRASEX + STRAWEI + ARMS)).
```

The variables OBE\_FU and OBE\_T0 will be shifted by the mean of OBE at T0 so that the intercept in the model reflects change in time. A closed-testing procedure will be used, meaning

---

 The planned dates are as follows: session 1/2 (week 1), session 3/4 (week 2), session 5/6 (week 3), session 7/8 (week 4), session 9 (week 5), session 10 (week 6), session 11 (week 7), session 12 (week 8),

that the initial comparison will be between the two intervention groups combined and the waiting group and the three pair-wise tests (fNIRS vs. wait control group, EEG vs. wait control group and fNIRS vs. EEG group) will be performed without adjustment if the global test is significant. If the global test is not significant, estimates and confidence intervals will still be provided for the contrasts in OBE, but no formal statistical test will be carried out. Estimates will be taken from the linear model and a Wald confidence interval will be used. Moreover, secondarily, the analogous analysis with effect size will be performed.

Missing data will be treated with multiple imputation using the R package “mice” (van Buuren and Groothuis-Oudshoorn 2011). The imputation variables will include the answer to the question “In how many of the situations in which you ate too did you feel you had lost control of your eating behaviour” (pre72). Sex, BMI and the stratification variable participation in a weight-loss programme will also be used. Fifty imputations will be performed.

To test the robustness of the results, the primary analysis will be repeated without imputation and pessimistic and optimistic scenarios will be considered.

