## 7 BIOMETRIC ASPECTS OF THE STUDY

### 7.1 Randomization algorithm

Randomization will be performed using an online tool programmed by the ZKS Leipzig (IFB Data centre).

The arm balance will be 1:1:1 and will be stratified by

- BMI (< 35.0 kg/m^2 vs. ≥ 35.0 kg/m^2)
- sex
- behavioral weight loss treatment status

A minimization algorithm based on Pocock and Simon will be used.

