### 7.4.2 Statistical error terms

The level of significance is set at  $\alpha = 5\%$ , aiming for a power of  $1 - \beta = 80\%$ .

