### 7.4.4 Sample size calculation

Based on a conservative effect size of 0.55 (compared to 0.65 quoted above), a t-test will have 80% power if 63 patients are analyzed (42 in the pooled intervention groups and 21 in the waiting control group), as determined using the software PASS 11. The width of the confidence intervals for the difference in means between two groups can then be expected to be about 0.88 SD for the pooled variance. The covariates incorporated into the analysis methods mean that the true power can be expected to be somewhat higher than that of the t-test reported here.

Taking into account a drop-out rate of about 20%, a total of 78 patients (26 per group) will be randomized.

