## 1 Introduction

The purpose of this document is to provide a detailed elaboration of the statistical analysis described in the protocol, including detailed procedures for the confirmatory analysis of the primary and secondary endpoints and other variables.

The SAP is based on the planned analysis specification as written in the study protocol, section 7 “Biometric Aspects of the Study”. All data will be analysed and reported in accordance with a recently published checklist (CRED-nf checklist; Ros et al., 2020). The table can be found in appendix 6.4.

The software package R Version 3.6.1 or higher will be used for statistical analyses. To reproduce online analysis, Turbo-Satori (TSI) 1.0.0. (BrainInnovation B.V., Maastricht, the Netherlands; Lührs & Göbel, 2017) will be used. Offline analyses of fNIRS data will be carried out with MATLAB R2018b using the Brain AnalyzIR Toolbox (Santosa et al. 2018); see Item 4e of the CRED-nf checklist).

Database variables are denoted by **this font and colour**.

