### 4.2.2 Analysis of continuous variables

Mean and SD will be provided at all available points in time for all valid values and after imputation. Imputation variables will include all data from the same “category” of secondary endpoints along with age and sex. If the imputation methods should fail to converge, then imputation variables will be successively removed starting with those having the weakest absolute value for linear correlation.

Variables at T1/T0WL will be analysed with linear models having the same structure as for the primary endpoint, but will include all three randomization arms from the outset (i.e. will not make use of the closed testing principle). Here too the variables will be shifted as with the primary endpoint.

Data for T0, T1 and T2 will be analysed for the intervention groups in a mixed model in which the stratification variables, time and group will be treated as fixed effects including the interaction between group and time. The patient ID will be treated as a random term. The model will be fit using restricted maximum likelihood (REML) and an unstructured variance-covariance matrix.

If multiple sub-scales of a questionnaire are tested formally, then Bonferroni-Holm correction for multiplicity will be used.

---

 The original German reads „In wie vielen dieser Situationen, in denen Sie zu viel gegessen haben, hatten Sie das Gefühl, die Kontrolle über Ihr Essverhalten verloren zu haben (während des Essens)?“

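### Centring only the two OBE variables does not make the intercept the change over time; with stratification factors and arm uncentred, it describes one reference cell in one unnamed arm.

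*SAP*

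**What the plan says.** SAP 4.1 gives the primary model as "anova(lm(OBE_FU ~ OBE_T0 + STRABMI + STRASEX + STRAWEI + ARMS", closed by the final brackets. `OBE_FU` and `OBE_T0` are to be "shifted by the mean of OBE at T0 so that the intercept in the model reflects change in time". The same section says "Estimates will be taken from the linear model and a Wald confidence interval will be used". SAP 4.2.2 applies the device to the continuous secondary endpoints, now with all three arms from the outset: "Here too the variables will be shifted as with the primary endpoint".

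The software is R (SAP 1: "The software package R Version 3.6.1 or higher will be used for statistical analyses"). Protocol 7.1 has three two-level stratification factors: BMI below or at least 35 kg/m², sex, and behavioral weight-loss treatment status. Neither document states a contrast coding, reference levels, a centring of the factors, or a marginal mean.

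**The concern.** An intercept is the fitted value when every other term is zero. Shifting the two OBE variables puts zero baseline at the average patient and puts the outcome on a change scale. It does nothing to the four remaining terms. With R's default coding, zero on those terms means one of eight stratum cells in one arm. The SAP does not name the arm, and it may differ between the pooled two-group comparison in 4.1 and the three-arm models in 4.2.2.

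Change over time is of interest in its own right: Protocol 2.2 lists temporal as well as group comparisons among the secondary objectives. The intercept is the only model-based change that SAP 4.1 offers, and the mixed model in 4.2.2 covers only the intervention groups, so it gives no change for the waiting arm. An analyst who followed the sentence would quote the intercept row as the change in time. That figure would answer a narrower question, with a wider interval.

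**Working it through.** The plan gives no figure for the intercept, so there is none to reproduce. Its only design figure, 80% power with 63 analysed (Protocol 7.4.4), concerns a between-arm test and is not used here.

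**Inputs from the documents.** Model and shift (SAP 4.1); three binary strata and 1:1:1 allocation (Protocol 7.1); 26 per arm randomised, 21 per arm analysed (Protocol 7.4.4).

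**Assumed, because the documents give none.** Stratum proportions, stratum effects and the baseline correlation.

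**Step 1: what the intercept is.** Let m be the T0 mean, y = OBE_FU − m and x = OBE_T0 − m. The model is y = α + βx + γ₁S₁ + γ₂S₂ + γ₃S₃ + arm effect + error, with each S coded 0/1. At x = 0, all S = 0 and the reference arm, α = E(OBE_FU) − m for that cell. If p_j is the proportion at S_j = 1, the reference arm's adjusted mean change is α + Σp_jγ_j. So

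α − (adjusted mean change) = −Σp_jγ_j,

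which is zero only if the weighted stratum effects cancel. Swapping the reference level of one factor moves α by that factor's γ.

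**Step 2: bias, by example.** Assume a true change of −2 OBEs in the reference arm, residual SD 7, p = 0.5/0.8/0.5 and each γ = +2. Then Σp_jγ_j = 1.8 × 2 = 3.6 and the intercept targets −2 − 3.6 = −5.6. In 500 simulated trials of 26 per arm it averaged −5.7, and the centred intercept −2.0. The mean SEs were 2.48 and 1.40. With effects +3, −3, +3 the sum is 1.5 − 2.4 + 1.5 = 0.6, and the intercept averaged −2.7. The sign pattern therefore decides whether the bias is large or small.

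**Step 3: precision.** With n per arm, N = 3n, and strata uncorrelated with each other, with arm and with baseline, Var(γ̂_j) = σ²/[N p_j(1 − p_j)]. Hence

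- centred: Var = σ²/n;
- uncentred: Var = σ²[1/n + (1/N) Σ p_j/(1 − p_j)].

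SEs in residual SDs at 26 per arm (N = 78):

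| p (BMI / sex / weight-loss treatment) | Σ p/(1−p) | uncentred | centred | ratio |
|---|---|---|---|---|
| 0.3 / 0.1 / 0.3 | 0.97 | 0.226 | 0.196 | 1.15 |
| 0.5 / 0.5 / 0.5 | 3.00 | 0.277 | 0.196 | 1.41 |
| 0.5 / 0.8 / 0.5 | 6.00 | 0.340 | 0.196 | 1.73 |
| 0.7 / 0.9 / 0.7 | 13.67 | 0.462 | 0.196 | 2.36 |

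For example, 50/50 strata give √(1/26 + 3/78) = √0.0769 = 0.277. Relabelling sex in the third row (0.8 to 0.2) lowers its SE to 0.259.

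To express these in outcome SDs with baseline correlation 0.5, multiply by √(1 − 0.25) = 0.866. Centred: 0.196 × 0.866 = 0.17 at 26 per arm and 0.218 × 0.866 = 0.19 at 21. Uncentred at 0.5/0.5/0.25 and 26 per arm: Σ = 2.33, √(1/26 + 2.33/78) × 0.866 = 0.23. Uncentred at 0.5/0.8/0.25 and 21 per arm: Σ = 5.33, √(1/21 + 5.33/63) × 0.866 = 0.31. Simulation, which adds chance imbalance, gave about 0.22 to 0.33 SD uncentred against 0.17 to 0.19 SD centred.

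**Step 4: other codings.** Sum coding gives an unweighted average over strata and arms (−5.3 in the +2 example). Strata entered as numeric 1/2 codes would refer to a cell that does not exist. Neither is the mean change.

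**Step 5: arm contrasts.** Across the simulated trials these differed by less than 1e-13 between unshifted, shifted and centred fits.

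**Step 6: what centring leaves open.** The model SE treats m as fixed. For population change, (1 − β)²·Var(T0)/N should be added. With β = 0.5, unit SDs and 21 per arm, the variance ratio is 1 + (0.25/63)/(0.75/21) = 1.11, so the SE is too small by √1.11 = 1.054, and a nominal 5% test rejects in 2[1 − Φ(1.96/1.054)] = 6.3%. Simulation gave about 6 to 8%.

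**The case against.** The strongest reply is that nothing planned depends on the intercept. SAP 4.1 names its tests: pooled intervention against waiting, then the three pairwise comparisons. It promises estimates and intervals for those contrasts. The listed `anova` call has no intercept row. The primary question in Protocol 2.1 and 7.3 is between groups, and those results do not change at all. Change over time is also described elsewhere: descriptive statistics by arm (SAP 4), means and SDs at each time point for the continuous secondary variables (4.2.2), and a T0 to T2 mixed model for the intervention groups. On this view the sentence only says, loosely, that the outcome has been put on a change scale.

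Most of that stands. A reader might infer that the trial will report and test a wrong within-arm change for the primary and every continuous secondary endpoint. The documents do not support this: the intercept is given a meaning but is not listed as an output or a test. Nor can a false-rejection rate be attached to it. With three stratum effects of 0.5 SD and no mean change, an intercept test rejected in about 63% of simulated trials when the effects had the same sign and about 6% when one was reversed (21 per arm, p = 0.5/0.8/0.25). Over wider assumptions the range was about 5% to 84%. A reader might also suppose that the intercept rests on the one to three patients in its cell. It does not: the model is additive and borrows from all patients.

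What does not stand is that the sentence is merely loose. It tells the analyst how to read a coefficient, that reading is wrong under every coding considered, and the waiting arm has no other model-based change.

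**Conclusion.** The interpretation in SAP 4.1, carried into 4.2.2, is wrong as written. If the intercept were used as stated, the change over time would be off by −Σp_jγ_j, an amount the documents do not allow us to estimate, and its SE would be about 0.22 to 0.33 SD instead of 0.17 to 0.19 SD. Those SEs assume a baseline correlation of 0.5, 21 to 26 per arm and illustrative stratum proportions; over a broader set of proportions the loss is 1.15 to 2.36 times. The description of the reference cell assumes R's default coding, which the model call implies but the SAP does not state.

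The confirmatory test, the arm contrasts and their intervals are not touched, and no test of the intercept is planned. The correction is therefore worth considering, not essential.

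**What to change.** In SAP 4.1 and 4.2.2:

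- Delete or correct the statement that the intercept gives the change over time.
- Centre the three stratum indicators at their sample proportions (0/1 minus the mean), or keep them as factors and use marginal means with proportional weights. The default equal weights in `emmeans` would not give the average over the trial population.
- Report the adjusted mean change for each arm, naming the arm, with its confidence interval.
- State that the ordinary model interval treats the sample T0 mean as fixed and is slightly too narrow for population change, or compute the SE of the change directly.

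The cost is about one sentence and one line of code. Between-arm results stay identical. The one small drawback is the mild undercoverage named in the last item.
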